9.4.3.2 Clinical Laboratory Data

Descriptive statistics will be used to summarize the change from baseline for laboratory tests by treatment group for each visit. Baseline is defined as the last nonmissing value obtained at a scheduled visit on or before Day -1. If the Day -1 measurement is missing, the baseline value will be the last nonmissing measurement from the screening visit (the previous scheduled visit). The incidence of potentially clinically significant changes and abnormalities in clinical laboratory test parameters will be summarized by treatment group. Clinical laboratory test data will be presented in listings.

9.4.3.3 Physical Examination and Vital Signs Data

Physical examination and vital signs data will be presented in listings.

The change from baseline for vital signs will be summarized by treatment group and visit using descriptive statistics. The incidence of potentially clinically significant values in vital sign parameters will be presented in listings.

9.4.3.4 Electrocardiogram Data

Electrocardiogram data will be presented in listings. The change from baseline in ECG parameters will be summarized by treatment group and visit using descriptive statistics. The incidence of potentially clinically significant changes and abnormalities in ECG evaluations will be summarized.

9.4.3.5 Suicidality Monitoring

The C-SSRS data will be analyzed for evidence of any treatment-emergent issues related to suicidal ideation or behavior. The incidence of suicidality, suicidal behavior, and suicidal ideation will be summarized by treatment group and visit. No inferential statistical analyses will be performed.

9.4.4 Other Analyses

9.4.4.1 Analysis of Demographic and Baseline Characteristics

Baseline demographic characteristics including age, race, ethnicity, sex, weight, height, and BMI will be summarized by treatment group using descriptive statistics for Part 1 and Part 2, separately.

9.4.4.2 Pharmacokinetic Analyses

OPC-167832 plasma concentrations will be listed by subject and summarized using descriptive statistics (N, mean, median, standard deviation, percentage coefficient of variation, minimum, and maximum) by treatment and timepoint. The trough plasma concentration of itraconazole, hydroxy-itraconazole, and carbamazepine will be listed by subject and summarized using descriptive statistics, as applicable.

Noncompartmental PK analysis will be performed to estimate the PK parameters for OPC-167832. Values of C_{\max} , AUC_t , AUC_{∞} , time to maximum (peak) plasma concentration (t_{\max}), apparent clearance of drug from plasma after extravascular administration (CL/F), body weight normalized CL/F, terminal phase elimination half-life ($t_{1/2,z}$) are planned. Other PK parameters, including those for metabolites, may be reported depending on the concentration data collected. Pharmacokinetic parameters

will be summarized by treatment and timepoint using the same descriptive statistics as for concentrations plus geometric mean. Values of t_{\max} will be summarized as median, minimum, and maximum.

CCI

9.5 Interim Analysis and Adaptive Design

No interim analysis or adaptive design are applicable.

9.5.1 Independent Data Monitoring Committee

Not applicable.

10 Supporting Documentation and Operational Considerations

10.1 Appendix 1: Regulatory, Ethical, and Trial Oversight Considerations

10.1.1 Ethics and Responsibility

This trial must be conducted in compliance with the protocol, Food and Drug Administration (FDA) regulations, applicable ICH Good Clinical Practice (GCP) guidance, international ethical principles derived from the Declaration of Helsinki and Council for International Organizations of Medical Science (CIOMS) guidelines, and applicable local laws and regulations. Each trial site will seek approval/favorable opinion by an IRB according to regional requirements, and the investigator will provide that documentation to the sponsor. The IRB will evaluate the ethical, scientific, and medical appropriateness of the trial. Further, in preparing and handling the eCRF, IRE and any safety information, the investigator, subinvestigator, and their staff will take measures to ensure adequate care in protecting subject privacy. To this end, a subject identifier (ID) will be used to identify each subject.

Financial aspects, subject insurance, and the publication policy for the trial will be documented in the agreement between the sponsor and the investigator.

10.1.2 Informed Consent

Informed consent will be freely obtained from all subjects (or their guardian or legally acceptable representative, as applicable for local laws). The ICF will be approved by the same IRB that approves this protocol.

Each ICF will comply with the ICH (International Council for Harmonisation GCP Guidelines, and local regulatory requirements. The investigator will ensure that the sponsor reviews and authorizes any written site-specific ICF used in the trial before submission to the IRB. In support of the site's standard process for administering informed consent, this trial will also allow for eICF as a tool within applicable regions and trial sites. The eICF utilizes the IRB-approved site-specific ICF to offer subjects an enhanced platform to review and understand their rights as a research subject as well as required trial procedures. When possible, trial sites will have subjects review and sign the eICF prior to starting any trial procedures; however, if local regulations do not allow for use of the electronic format, subjects may continue in the trial utilizing the standard paper and wet ink signature process.

Investigators may discuss trial availability and the possibility for entry with a potential subject without first obtaining consent. However, informed consent must be obtained and

documented before initiation of any procedures that are performed solely for the purpose of determining eligibility for this trial, including withdrawal from current medication(s).

Potential subjects are free to refuse entry into the trial, or withdraw from the trial at any time, without justification, and there will be no consequences to their further care.

Prospective trial subjects will be provided with controlled access to the electronic ICF (eICF) application by trial site staff. When the trial site staff and the subject agree that the subject has enough information to make an informed decision to participate, the subject will electronically sign in the eICF application and an electronic date and timestamp will be applied to the signature. The subject will be given a printed, signed copy of the ICF. Any other parties required by the IRB (trial site staff, witnesses, or legally authorized representative) are also required to sign electronically and these signatures will be stored with the eICF in accordance with the ICH GCP Guideline and local regulatory requirements/guidelines. These signatures cannot be altered, removed, or copied.

Once appropriate essential information has been provided and fully explained in layman's language to the subject by the investigator (or a qualified designee), and it has been documented that the subject has had the opportunity to ask questions, the IRB-approved written ICF will be signed and dated by both the subject and the person obtaining consent (investigator or designee), as well as by any other parties required by the IRB. The subject will receive a copy of the signed ICF; the original shall be kept on file by the investigator.

Subjects may be asked to sign additional ICFs if the protocol is amended and the changes to the protocol result in additional information that needs to be provided to the subjects, so that they can make a knowledgeable and voluntary decision on continued trial participation. Female partners of male subjects who become pregnant during the course of the trial may be asked to sign additional ICFs in order to collect additional information regarding the non-subject partner and fetus.

CCI

10.1.3 Recruitment Strategy

Methods for subject recruitment include, but are not limited to: media (ie, television, radio and newspaper), physician referrals, press releases, fliers, random mailings, cold calls and the internet. Methods will be selected before study start.

10.1.4 Confidentiality

All information generated in this trial will be considered confidential and will not be disclosed to anyone not directly concerned with the trial without the sponsor's prior

written permission. Subject confidentiality requirements of the region(s) where the trial is conducted will be met. However, authorized regulatory officials and sponsor personnel (or their representatives) may be allowed full access to inspect and copy the records, consistent with local requirements. All trial intervention(s), subject bodily fluids, and/or other materials collected shall be used solely in accordance with this protocol, unless otherwise agreed to in writing by the sponsor.

Subjects will be identified only by unique subject ID in the eCRF. If further subject identification is required, subjects' full names may be made known to a regulatory agency or other authorized officials, if necessary, subject to local regulations.

10.1.5 Quality Control and Quality Assurance

10.1.5.1 Monitoring

The sponsor has ethical, legal, and scientific obligations to follow this trial in accordance with established research principles, the applicable ICH GCP guidance, and applicable regulatory requirements and local laws. As part of a concerted effort to fulfill these obligations (maintain current personal knowledge of the progress of the trial), the sponsor's monitors will visit the site during the trial, as well as communicate frequently via telephone, e-mail, and written communications. In addition, all investigators and trial site personnel will undergo initial and ongoing training for this particular trial, and this training will be clearly documented.

10.1.5.2 Auditing

The sponsor's Quality Assurance Unit (or representative) may conduct trial site audits. Audits will include, but are not limited to, trial intervention supply, presence of required documents, the informed consent/assent process, site operations, delegation of authority and training, and a review of the eCRF with source documents, as applicable. The investigator will agree to cooperate and participate with audits.

Regulatory authorities may inspect the investigator site during or after the trial. The investigator will cooperate with such inspections and will contact the sponsor immediately if such an inspection occurs.

10.1.6 Protocol Deviations

In the event of a significant/major deviation from the protocol due to an emergency, accident, or mistake (eg, violation of informed consent/assent process, trial intervention dispensing or subject dosing error, treatment assignment error, subject enrolled in violation of eligibility criteria or concomitant medication criteria), the investigator or designee will contact the sponsor or designee at the earliest possible time by telephone or

via e-mail. The investigator and sponsor (or designee) will come as quickly as possible to a joint decision regarding the subject's continuation in the trial. This decision will be documented by the investigator and the sponsor (or designee) and reviewed by the site monitor.

Any major protocol deviation will be recorded in the eCRF along with the start date and details of the deviation.

10.1.7 Records Management

10.1.7.1 Source Documents

Source documents are defined as the results of original observations and activities of a clinical investigation. Source documents will include but are not limited to medical records, electronic data, screening logs, progress notes, paper-based assessments and scales, and recorded data from automated instruments or applications. All source documents pertaining to this trial will be maintained by the investigators and made available for direct inspection by authorized persons.

Investigator(s)/institution(s) will permit trial-related monitoring, audits, IRB review, and regulatory inspection(s) by providing direct access to source data/documents by authorized persons as defined in the ICF. In all cases, subject confidentiality must be maintained in accordance with local regulatory requirements.

10.1.7.2 Data Collection

During each subject's visit to the site, an investigator or their designee participating in the trial will record information to document all significant observations. At a minimum, these notes will contain:

- Documentation of the informed consent/assent process, including any revised ICFs;
- Documentation of the investigator's decision to enroll the subject into the trial, the review of all inclusion/exclusion criteria prior to trial intervention administration, and confirmation of the subject's actual participation in the trial;
- Documentation of baseline and demographic characteristics (eg, age, weight, BMI, sex, race, ethnicity);
- The date of the visit and the corresponding Visit or Day in the trial schedule;
- General subject status remarks, including any significant medical findings. The severity, frequency, duration, action taken, and outcome of any AEs and the investigator's assessment of relationship to trial intervention must also be recorded;
- Any changes in concomitant medications or dosages;
- A general reference to the procedures completed, including dosing and trial intervention compliance;

- The signature (or initials) and date of the investigator (or designee) who made an entry in the medical record.

In addition, any contact with the subject via telephone or other means that provides significant clinical information will also be documented in the progress notes as described above.

Source documents and source data will be captured electronically (where permitted by local regulation) in this trial and will meet the same fundamental elements of data quality (eg, attributable, legible, contemporaneous, original, accurate, and complete) as paper records. These data will be collected into a system that is fully validated according to 21 CFR Part 11. Changes to the data will be captured by an automatic audit trail.

Designated trial site staff will not be given access to the electronic source system until they have been appropriately trained. Information to be originally captured and reviewed electronically shall include details of the subject visit and the protocol required assessments performed as a part of these visits, medical history, AEs, and concomitant medications. Because this trial is using an electronic source record as the original point of data capture, there is no additional data entry step for the trial site for data collected directly into the application, rather, the electronic source record directly populates the trial database.

Some data may be captured via paper and then entered into the eSource system. These and any other data treated in this manner will be source data verified per the monitoring plan and the location of the source data (ie, eSource, paper, or a local electronic system) will be documented before the trial start. Any changes to information in paper source documents will be initialed and dated on the day the change is made by a trial site staff member authorized to make the change. Changes will be made by striking a single line through erroneous data (so as not to obliterate the original data), and clearly entering the correct data (eg, ~~wrong data~~ right data). If the reason for the change is not apparent, a brief explanation for the change will be written in the source documentation by the investigator or their designee.

Another exception will be safety laboratory [or central ECG data], where the official source documentation will be considered the report issued by the analyzing laboratory.

Remote monitoring of the original electronic source records will take place; however, on-site monitoring inspections will continue to take place in order to review data entry of source documentation directly captured on paper and transcribed into the system, to ensure protocol adherence, to assess trial site operational capabilities and to perform other monitoring activities that cannot be performed remotely.

At the end of the trial, the investigator must certify that the data entered into the eSource application are complete and accurate. After database lock, the investigator will receive an electronic copy of the subject data.

10.1.7.3 File Management at the Trial Site

The investigator will ensure that the trial site file is maintained in accordance with applicable ICH GCP guidance and as required by applicable local regulations. The investigator/institution will take measures to prevent accidental or premature destruction of these documents.

Food and Drug Administration regulations require all investigators participating in clinical drug trials to maintain detailed clinical data for one of the following periods:

- A period of at least 2 years after the date on which a New Drug Application is approved by the FDA;
- A period of 2 years after the sponsor has notified the FDA that investigation with this drug is discontinued.

The investigator must not dispose of any records relevant to this trial without either (1) written permission from the sponsor or (2) provision of an opportunity for the sponsor to collect such records. The investigator will be responsible to maintain adequate and accurate electronic or hard copy source documents of all observations and data generated during this trial including any data clarification forms received from the sponsor. Such documentation is subject to inspection by the sponsor and relevant regulatory authorities. If the investigator withdraws from the trial (eg, due to relocation or retirement), all trial-related records should be transferred to a mutually agreed-upon designee within a sponsor-specified timeframe. Notice of such transfer will be given to the sponsor in writing.

10.1.7.4 Dissemination of Clinical Trial Data

Clinical study reports, periodic safety reports, and clinical trial summary reports will be disclosed after review by regulatory authorities. This includes access to clinical study reports from trials with negative outcomes and from terminated development programs.

10.1.7.5 Publication Authorship Requirements

Authorship for any Otsuka-sponsored publications resulting from the conduct of this trial will be based on International Committee of Medical Journal Editors (ICMJE) authorship criteria (<http://www.icmje.org/recommendations>). According to ICMJE guidelines, one may be considered an author only if the following criteria are met:

- 1) Substantial contributions to the conception or design of the work; or the acquisition, analysis, or interpretation of data for the work; AND
- 2) Drafting the work or revising it critically for important intellectual content; AND
- 3) Final approval of the version to be published; AND
- 4) Agreement to be accountable for all aspects of the work in ensuring that questions related to the accuracy or integrity of any part of the work are appropriately investigated and resolved.

All authors must meet the above criteria, and all who qualify for authorship based on the above criteria should be listed as authors.

Investigators or other personnel involved in the conduct of the trial who do not qualify for authorship may be acknowledged in publications resulting from the trial. By agreeing to participate in the trial, investigators or other personnel involved in the conduct of the trial consent to such acknowledgment in any publications resulting from its conduct.

10.2 Appendix 2: Clinical Laboratory Tests

The tests detailed in [Table 10.2-1](#) will be performed.

Table 10.2-1 Clinical Laboratory Assessments	
Hematology: Hemoglobin Hematocrit Mean corpuscular hemoglobin concentration Mean corpuscular volume RBC count WBC count (absolute and differential) Platelets Urinalysis: Specimen appearance Color Occult blood Glucose Microscopic analysis, if indicated, WBC/RBC counts per high powered field pH Protein Specific gravity Additional Tests: Urine or serum pregnancy for females of childbearing potential Follicle-stimulating hormone for postmenopausal females Serology (hepatitis B surface antigen, hepatitis C antibodies, human immunodeficiency virus)	Serum Chemistry: Alkaline phosphatase Alanine aminotransferase Aspartate aminotransferase Bilirubin, total (with reflex if elevated) Blood urea nitrogen Calcium Cholesterol Creatinine Gamma glutamyl transferase Glucose Lactate dehydrogenase Magnesium Potassium Protein, total Sodium Triglycerides Drug Screen (all items in urine except where noted) Alcohol Amphetamines Barbiturates Benzodiazepines Cannabinoids Cocaine Cotinine (urine or serum) Methadone Opiates Phencyclidine Propoxyphene

RBC = red blood cell; WBC = white blood cell.

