2.3 Known and Potential Risks and Benefits

Subjects will receive no health benefit from participation in this trial.

Single oral doses up to 480 mg OPC-167832 were well tolerated during Trial 323-201-00001; there were no serious or severe AEs and no subjects were discontinued from the trial due to a treatment-emergent AE. One subject did decide to withdraw consent after occurrence of the nonserious and mild AEs of arthralgia, pain in extremity, and ecchymosis.¹ There was a slight negative correlation observed between changes in QT interval corrected for heart rate using Fridericia's formula (QTcF) from baseline and placebo, and OPC-167832 plasma concentrations. There is currently 1 ongoing trial (Trial 323-201-00003) that is evaluating the safety of OPC-167832 in adult subjects with uncomplicated DS pulmonary TB. There was 1 SAE of haemoptysis (3 mg group in Stage 1), which led to discontinuation of investigational medicinal product (IMP). This SAE was not considered to be causally related to the IMP but as a complication of the underlying pulmonary TB. There was 1 SAE of anal abscess (30 mg OPC-167832 and 400 mg bedaquiline group in Stage 2), which led to discontinuation of IMP and was considered unrelated to the IMP.¹

In 1-, 4-, and 26-week toxicity studies in rats, no drug-related deaths occurred in either males or females at any dose tested. Suppressed body weight gain and/or decreased food consumption were observed and increases in total cholesterol and phospholipids and decreases in creatinine were observed at 1 week. These changes showed reversibility or a tendency for reversibility.

In 1-, 4-, 13- and 39-week toxicity studies in dogs, no treatment related deaths occurred in either males or females at any dose tested. Increases in creatinine kinase, alanine aminotransferase (ALT), aspartate aminotransferase (AST), lactate dehydrogenase, and potassium were observed in the 4-week toxicity study at the highest dose (2000 mg/kg/day). Increases in total cholesterol and phospholipids were also observed in the 4- and 13-week toxicity studies at doses of 100 mg/kg/day and higher. In the 4-week toxicity study, slight prolongation of QT interval and QTc was observed at Week 4 in both sexes at 2000 mg/kg/day. However, no prolongation of QT interval and QTc was noted in the 13-week toxicity study in either sex at up to 100 mg/kg.

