In 4- and 13-week repeated dose oral toxicity studies in dogs, decreased body weight or suppressed body weight gain, or both, and decreased food consumption were observed. In histopathological examination, degeneration of muscle was fiber observed in both sexes at doses of 10 mg/kg and greater. These changes showed reversibility or a tendency for reversibility.¹

Safety information on the CYP inhibitors and inducers that will be used in this trial can be found in their United States Prescribing Information (USPI).

The trial site will receive updated versions of the IB, when available, and the trial site should always refer to the most current version as needed.

3 Objectives and Endpoints

Table 3-1 Trial Objectives and Endpoints	
Objectives	Endpoints
Primary: To assess the potential for CYP-mediated drug-drug interactions with OPC-167832: 
 Inhibition of OPC-167832 metabolism via CYP3A by itraconazole Induction of OPC-167832 metabolism via CYP3A by carbamazepine 	Primary: OPC-167832 PK: C_{max} , AUC_t , and AUC_{∞}
Secondary: To assess the safety and tolerability of OPC 167832 administered alone or in combination with itraconazole or carbamazepine	Secondary: Safety: AEs, clinical laboratory tests, vital signs, physical examinations, 12-lead ECGs, and C-SSRS (Part 2 only)

AE = adverse event; AUC_{∞} = area under the concentration-time curve from time zero to infinity;

AUC_t = area under the concentration-time curve calculated to the last observable concentration at time t ; C_{max} = maximum (peak) plasma concentration of the drug; C-SSRS = Columbia-Suicide Severity Rating Scale; CYP = cytochrome P450; ECG = electrocardiogram; PK = pharmacokinetics.

Section 9.4 describes the statistical analysis of the endpoints.

4 Trial Design

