4.3 Dosing Rationale

The trial is designed with 2 parts to separately evaluate the potential for DDIs between OPC-167832 and either itraconazole (inhibition of CYP3A, Part 1) or carbamazepine (induction of CYP3A, Part 2). The OPC-167832 dose of 30 mg will be administered CCI under fasted conditions. OPC-167832 CCI 30 mg was considered a clinically-relevant dose according to the preliminary results from the multiple-ascending dose/early bactericidal activity trial (Trial 323-201-00003). The potential higher plasma exposure of approximately 5- to 6-fold (C_{max} and AUC) with itraconazole would be within the safety margin of highest tested clinical dose of 480 mg of OPC-167832 (Trial 323-201-00001).

Itraconazole (200 mg given QD as 10-mg/mL solution) is the recommended regimen for strong CYP3A inhibition.⁵ A loading dose of 200 mg BID every 12 hours on the first day of itraconazole administration (Day 8) followed by QD administration of 200 mg allows for more rapid attainment of itraconazole steady-state conditions. Once daily dosing of itraconazole will be continued through Day 25.

Carbamazepine was selected for administration in Part 2 because it is cited as a CYP3A inducer in the Food and Drug Administration table “Examples of clinical inducers for P450-mediated metabolisms (for concomitant use clinical DDI studies and/or drug labeling) (9/26/2016)”.⁶ Literature studies conducted in healthy subjects used carbamazepine doses ranging from 200 to 1200 mg/day, with the majority of studies conducted with 400 mg/day or 600 mg/day.⁷ The physiologically based PK simulation showed that 600 mg/day approached the plateau of induction. Given titration may be needed to improve the tolerability and reduce drop-out rate, carbamazepine was usually initiated from 100 mg BID and titrate to 300 mg BID over 3 to 7 days and then maintain at 300 mg BID for 14 days to reach the maximum effect. Therefore, 100 mg BID carbamazepine will be administered for 3 days, followed by dosing of 200 mg BID for 3 days, then 300 mg BID for 10 days. Twice daily dosing of 300 mg carbamazepine will be continued through Day 31.

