8.6.6 Potential Serious Hepatotoxicity

For a subject who experiences an elevation in AST or ALT that is ≥ 3 times the upper limit of normal (ULN), a total bilirubin level should also be evaluated. If the total bilirubin is ≥ 2 times the ULN, complete an IRE form with all values listed and report as an AE in the eCRF. Details regarding the follow-up of IREs are included in [Section 8.6.8.2](#).

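### The laboratory panel measures four of the five markers that rose together in dogs but not creatine kinase, so an isolated AST or ALT rise could be traced to muscle or liver only indirectly

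*Protocol*

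**What the plan says.** Protocol Section 2.3 gives two separate dog findings. The first is biochemical: "Increases in creatinine kinase, alanine aminotransferase (ALT), aspartate aminotransferase (AST), lactate dehydrogenase, and potassium were observed in the 4-week toxicity study", at the top dose of 2000 mg/kg/day. The enzyme is printed as creatinine kinase; I read it as creatine kinase. The second is histological, from the 4- and 13-week repeated-dose studies: "degeneration of muscle was fiber observed in both sexes at doses of 10 mg/kg and greater". The paragraph with the histology closes: "These changes showed reversibility or a tendency for reversibility".

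Section 4.3 deals with exposure in Part 1. "The potential higher plasma exposure of approximately 5- to 6-fold" for Cmax and AUC with itraconazole is said to be one that "would be within the safety margin of highest tested clinical dose of 480 mg of OPC-167832".

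Section 8.5.1 states that the laboratory tests are those of Section 10.2. The serum chemistry column of Table 10.2-1 ends "Cholesterol Creatinine Gamma glutamyl transferase Glucose Lactate dehydrogenase Magnesium Potassium Protein, total Sodium Triglycerides". Above that stand alkaline phosphatase, ALT, AST, total bilirubin, blood urea nitrogen and calcium.

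Section 8.6.6 says that, for an "elevation in AST or ALT that is ≥ 3 times the upper limit of normal (ULN), a total bilirubin level should also be evaluated"; an immediately reportable event follows only if bilirubin is also at least 2 times the ULN. SAP Section 10.8 is wider. Its incidence table and listing take any subject who meets one or a combination of its two criteria, so transaminases alone are enough.

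**The concern.** The risk section names five laboratory markers that moved together in dogs. The panel follows four of them, and the one it leaves out is the one that points to muscle. The protocol gives no reason for the omission.

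What is at stake is interpretation of the secondary safety objective. AST, ALT, LDH and potassium are not specific to any one tissue. If a muscle effect occurred under the higher Part 1 exposure, it would show in the planned data as a transaminase or LDH rise. At 3 times the ULN or more, that rise would be counted in a table meant to signal liver injury, with no muscle marker beside it. The reader of the study report would have to judge its origin from hepatobiliary markers and whatever extra tests the investigator happened to order.

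**Working it through.** This is a comparison of passages rather than a calculation. The one figure in the plan that bears on it, the 5- to 6-fold rise, cannot be reproduced, because the documents give neither the simulation nor the exposure data behind it.

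**1. Dog markers against the panel** (Section 2.3 against Table 10.2-1)

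| Marker that rose in dogs | In the 16-analyte panel? |
|---|---|
| ALT | yes |
| AST | yes |
| LDH | yes |
| Potassium | yes |
| Creatine kinase | no |

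Four of five are measured.

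**2. Is creatine kinase added elsewhere?** It is in neither schedule of assessments nor Section 8.5. Section 8.6.1 lets the investigator ask for additional tests to verify a result, without naming creatine kinase. Footnote b of Table 1.3-2 concerns haematology in Part 2. SAP Appendix 2 has a creatine kinase row (grade 1 from 3 times the ULN) because the whole DAIDS table is reproduced, but SAP Appendix 1 links no protocol assessment to it. Appendix 1 also links LDH to the DAIDS row for lactate, a different analyte, so LDH has no valid grade either.

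**3. Where an isolated transaminase rise would go.**
- Section 8.6.6: AST or ALT at least 3 times the ULN prompts a bilirubin check. With normal bilirubin there is no immediately reportable event.
- SAP Section 10.8: the same value alone puts the subject in the liver table and listing.
- Below 3 times the ULN: AST and ALT are graded by DAIDS from 1.25 times the ULN and reviewed by the investigator.

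**4. Which draws could be informative** (Tables 1.3-1 and 1.3-2)
- Part 1, doses on Days 1 and 15: draws at screening and on Days -1, 1, 2, 15, 16 and 26. Day -1 is the laboratory baseline (SAP Section 10.3). Day 2 follows the dose given alone. Days 16 and 26 follow the dose given with itraconazole. The draw time on Days 1 and 15 is not stated; if predose, only Days 16 and 26 reflect the raised exposure.
- Part 2, doses on Days 1 and 25: draws at screening and on Days -1, 8, 11, 14, 25 and 32. Days 8 to 25 are predose, so they fall 8 - 1 = 7 to 25 - 1 = 24 days after the first dose. Only Day 32 follows the second dose, and this part tests induction, which would lower exposure.

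**5. How far the 480-mg dose reassures.** The dose ratio is 480/30 = 16. If exposure were proportional to dose, 5- to 6-fold would equal 150 to 180 mg, leaving a margin of 480/150 = 3.2 to 480/180 = 2.7. Section 2.2.2 says exposure rises less than in proportion. Assume a power model with exponent b, so that the exposure ratio is 16^b:

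| b (assumed) | 16^b |
|---|---|
| 0.9 | 12.1 |
| 0.8 | 9.2 |
| 0.7 | 7.0 |
| 0.6 | 5.3 |
| 0.5 | 4.0 |

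Cover for 5-fold needs b ≥ ln 5/ln 16 = 0.58, and for 6-fold b ≥ ln 6/ln 16 = 0.65. The documents do not give b, so the stated margin can be neither confirmed nor refuted from them.

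**The case against.** The case for leaving the panel alone has weight.

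- **The animal evidence is remote.** The dog findings came from repeated dosing; here each subject takes two single 30-mg doses, 14 or 24 days apart. The creatine kinase rise is reported only at 2000 mg/kg/day, which is 2000/10 = 200 times the lowest dose with muscle degeneration. The protocol does not link the two findings. This stands, and it leaves open whether creatine kinase would detect anything at trial exposures.
- **Human tolerability.** Single doses up to 480 mg were well tolerated, with no serious or severe adverse events. This stands, although Section 2.3 does not say whether creatine kinase was measured. The Investigator's Brochure may answer that; it was not available for this review.
- **Indirect markers exist.** A reader might infer that muscle effects go unmonitored, or that nothing collected could tell muscle from liver. The documents do not support that. GGT, alkaline phosphatase and bilirubin help to separate hepatobiliary from other causes, and creatinine and urine occult blood are measured too. Nor would a rise below 3 times the ULN be ignored: it is graded and reviewed, and recorded as an adverse event with causality if clinically significant.
- **The volunteer who withdrew.** A reader might take the arthralgia, pain in extremity and ecchymosis in Section 2.3 as a human muscle signal. The events are described as mild and nonserious, no dose or causality is given, and joint pain and bruising are not muscle findings.
- **The DAIDS row.** It does not show that creatine kinase testing was intended, since rows for CD4 counts and neonates are there as well.

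None of this explains why the named muscle marker is the one left out.

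**Conclusion.** The point holds in a limited form. The risk section and the panel do not match: four of the five markers are collected, none of them muscle-specific, and an isolated AST or ALT rise in the SAP 10.8 table could be attributed only indirectly.

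The size is modest. The higher-exposure argument concerns one dose in the 12 Part 1 subjects, and the 5- to 6-fold figure is a possibility in Section 4.3, not a forecast. To extend it to all 24 subjects would go beyond the documents. It would also overstate Section 8.6.6 to say that a muscle-origin rise would by itself trigger an immediate report, since bilirubin must be raised too.

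The conclusion rests on reading the printed enzyme name as creatine kinase, and on no separate manual adding the test. Sensitivity at trial exposures is unknown. This is a low-cost improvement; it does not invalidate the safety plan or touch the primary PK analysis.

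**What to change.** 1. Add creatine kinase to Serum Chemistry in Protocol Table 10.2-1, at the existing laboratory time points in both parts. The main value is in Part 1: Day -1 as baseline, then Days 2, 15, 16 and 26. In Part 2 it is Day 32 against Day -1.
2. Add a creatine kinase line to SAP Appendix 1 that points to the DAIDS row for high creatine kinase already in Appendix 2.
3. Show the concurrent creatine kinase value beside AST and ALT in the SAP Section 10.8 listing.

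If the sponsor prefers not to add the test, a sentence in the protocol saying why the indirect markers suffice would close the gap between Section 2.3 and Table 10.2-1.

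Cost: one more analyte on serum already drawn, with no new visit or venipuncture. With 7 scheduled laboratory occasions in each part including screening, that is 24 × 7 = 168 determinations in the enrolled subjects, plus those in screen failures. The downside is an occasional incidental rise. The bar on strenuous activity in Section 5.3.3, from 24 hours before check-in to the end of the trial, limits this, and each value can be read against Day -1.
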